**Data Analysis**

Independent t-tests will be used to examine demographic differences between the two groups. A 2 (limb) x 2 (group) ANOVA will be used to evaluate differences in strength, TMS, and fNIRS measures. Regression analyses will be used to determine the relationship between the CNS measures and quadriceps strength, and the relationship between the TMS and fNIRS measures.

**9. Compensation or Credit - Describe the amount and timing of any compensation or credit to participants. Identify the source of the funds to compensate participants**

*Each participant (≥18 years of age) will be paid \$100 for their participation in this study. Participants must complete both sessions to receive the compensation.*

*Each participant (<18 years of age) will receive \$50 for their participation in this study as they will only complete one session.*

**10. Risk to Participants - List the reasonably foreseeable risks, discomforts, or inconveniences related to participation in the research. Consider physical, psychological, social, legal, and economic risks.**

*Risks associated with Testing Procedures (TMS, strength testing)*

*There are no known long term risks of TMS. There is a very small risk of seizure, syncope, and change in auditory thresholds. A recent study examining adverse events of TMS concluded: "Our data suggest that single/paired-pulse and repetitive TMS, conducted within the published guidelines pose a very small increment over the background risks of everyday life to subjects without known risk factors." Screening potential participants for a prior history of seizures, syncope, and hearing impairments will allow us to exclude individuals at increased risk. Participants will be offered ear plugs if the sound from the TMS pulse is uncomfortable.*

*In the very unlikely event of a seizure, the following steps will be taken: 1) The participant will be positioned in the safest position to maintain an open airway (i.e. laying supine or side lying), 2) emergency personal will be contacted by dialing 911 (research assistant), 3) any objects will be moved away from the participant to prevent additional injury, 4) monitor vitals until emergency personal arrive.*

*Most subjects report no discomfort from TMS although some do report mild discomfort over the site of stimulation. Some subjects report a mild headache following the procedure. This typically resolves within 24 hours and can be treated with over the counter analgesics (i.e. Tylenol, ibuprofen). If subjects do experience discomfort over the stimulation site, the intensity of the stimulator can be reduced to minimize this. The session will be terminated immediately if the subject reports discomfort that is beyond their tolerance. Subjects may experience mild muscle soreness 24-48 hours after the testing session. This is a normal physiologic response to strength testing and strength training. There are no risks or discomfort associated with strength testing. Strength testing is performed at regular intervals after ACL reconstruction.*

*Risks associated with transcranial direct current stimulation (tDCS)*

*tDCS have been used in a growing number of laboratories worldwide since 1985. In the present protocol, only a non-significant risk protocol is being employed by using tDCS. tDCS is very safe and there have been very few incidences of adverse events with tDCS. A recent meta-analysis of adverse effects associated with tDCS reviewed 209 experiments (3836 subjects). The main adverse events were itching, tingling, headache, discomfort, and burning sensation. Poreisz et al summarized findings from 567 sessions involving 102 participants to demonstrate that adverse effects were quite minor in severity. For example, mean ratings of itching during stimulation were 1.6 out of 5. Similar ratings were given for tingling (1.74), burning (1.59), headache (1.4), pain (1.41), difficulties in concentrating (1.73), nervousness (1.0), and unpleasant sensation (1.24). The highest rated adverse effect was fatigue (2.17), although the authors note that this factor was likely influenced by the completion of sometimes monotonous tasks while also receiving tDCS.*

*There is a strong evidence that tDCS is extremely safe. A recent review reported that "To date, based on over a total 33,000 sessions and over 1000 subjects who received repeated tDCS sessions, there is no evidence for*

*irreversible injury produced by conventional tDCS protocols within a wide range of stimulation parameters ( $\leq 40$  min,  $\leq 4$  mA,  $\leq 7.2$  C). In our protocol, the dose of tDCS is significantly below the dose ( $\leq 2$  mA, 20 min) described here. An even more recent systematic review (2018) concluded that “Little evidence was found to suggest that repeated sessions of active tDCS poses increased risk to participants compared to sham tDCS within the limits of parameters used to date.” However, in case of an unlikely adverse event, we will have appropriate measures to ensure participant safety and comfort. If there is any discomfort during the tDCS procedure, we will double-check our electrodes and machine settings. In case of a headache/neck pain after tDCS, the participant will be advised to take an over-the-counter pain medication. In an unlikely event of skin burn, participant will be referred/ directed to a physician for medical management. Patient and/or his/her medical insurance will pay for the care. This will be made clear in the informed consent.*

*We will assess any discomfort or adverse event before, during or after tDCS in patients and age-matched controls. We do not anticipate any major adverse events. Only minor discomfort in less than 5% of subjects undergoing tDCS experience is transient headaches or soreness at the site of stimulation. These side-effects are believed to be due to stimulation of muscles and nerves near the stimulating coil. During and following every tDCS session, we will ask the participant about any incidence of headache. If the participant complains of any discomfort or pain during the tDCS session, the session will be terminated at once. Participants will be informed that if they should feel a tingling sensation below the electrodes. If they feel any other uncomfortable sensation such as burning, they should inform the investigators. If the participant informs us of uncomfortable sensation, we will ensure electrode/machine settings are correct. If the uncomfortable sensation continues, we will stop the procedure.*

*In order to ensure participant safety following the session, we will use the questionnaire proposed by Brunoni et al. 2011 after each session to record any adverse effects, and follow-up with participants the day after each session if they report scores of 3 (moderate) or 4 (severe) for any of the symptoms or side effects. Anyone self-reporting a severe effect (4) will be withdrawn from the study.*

Risks associated with stationary bike riding

*There is very minimal risk involved with stationary bike riding in our population of athletic individuals. Additionally, stationary bike riding is part of standard physical therapy early (prior to 4 months which is the earliest time that we would recruit a participant) after ACLR. During the intervention (stationary bike with tDCS), participant tolerance will be assessed subjectively (rating of perceived exertion, symptoms) at regular intervals, and the exercise will be terminated if signs or symptoms indicate poor tolerance. In addition, the protocol will include warm-up and cool down phases to minimize the risk of musculoskeletal injury. If required, the participants will be provided with water before, during or after the exercise.*

**11. Potential Benefits to Participants - Realistically describe the potential benefits that individual participants may experience from taking part in the research. Indicate if there is no direct benefit. Do not include benefits to society or others.**

*Results of the strength test will be provided to participants in both groups. The results of the strength test will benefit participants in the ACLR group as the findings indicate whether additional strengthening is required and if progression into the next stage of rehabilitation is warranted. The results do not provide any benefits to participants in the uninjured group.*

**12. Confidentiality - Describe the following measures to ensure the confidentiality of data: Who will have access to the data? Where and how data will be stored? How long the data will be stored? How and when will data be de-identified?**

*The primary investigator ([name]), coinvestigator ([name]), and doctoral students working as research assistants will have access to the data. Electronic data will be stored on the hard drive of the computer that runs the HUMAC NORM and a password protected University maintained server only assessable to [name]. Paper data records will be locked in file cabinets in [name] office. All data will be de-identified. A unique two-digit identifier will be randomly assigned to each participant. This code will be utilized on all of the data collection materials. De-identified data will be stored indefinitely.*

**13. Consent Process - Describe the process and procedures process you will use to obtain consent. Include a description of: who will be responsible for completing the consent process with participants, where the consent process will take place, how consent will be obtained; and if participants who do not speak English will be enrolled, describe the process to ensure that the oral and/or written information provided to those participants will be in their preferred language. Indicate the language that will be used by those obtaining consent.**

*Consent forms will be used and are attached for review. The PI will obtain consent from all participants.*

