*My previous work indicates that after ACLR patients demonstrate alterations in CSE as early as 2 weeks after surgery, and these alterations do not change during the course of post-operative rehabilitation ([name], in review, JOR; [name], in review, JOSPT). More specifically, patients after ACLR demonstrated reduced thresholds and altered excitability, which suggests that the corticospinal tract has a higher recruitment threshold with potentially steep activation curves. Reduced thresholds and steeper recruitment curves may limit a more graded activation of the quadriceps necessary for functional movement and stability. The fact that the alterations in CSE did not change from 2 weeks after surgery to a mean of 4.5 months after surgery suggests that current rehabilitation strategies are not addressing alterations in CSE. There is a need to investigate new neuromodulatory interventions, such as transcranial direct current stimulation, that have the potential to modify CSE and muscle performance in patients after ACLR.*

*Transcranial direct current stimulation (tDCS) increases short-term CSE and isometric strength in healthy participants and stroke survivors. In the proposed pilot study, tDCS will be used as an intervention to determine its effects on CSE and quadriceps muscle performance in patients recovering from ACLR. We will incorporate two measures of quadriceps performance, isometric strength and rate of torque development (RTD) as both measures are altered and related to functional outcomes after ACLR. However, to the best of my knowledge, no studies have determined the effectiveness of tDCS on CSE and quadriceps performance in patients after ACLR, and no studies to date have evaluated the relationship between multiple measures of quadriceps performance and CSE in patients after ACLR. Evaluating new interventions with potential to mitigate alterations in CSE (i.e. active motor thresholds (AMT) and slope of the recruitment curve (SLOPE)) and quadriceps muscle performance (i.e. isometric strength and RTD) in patients recovering from ACLR are critical to improving outcomes in this population. Therefore, the aims of this study are to:*

**Aim 1:** Determine the effects of a single session of tDCS on two measures of CSE and two measures of quadriceps performance in patients after ACLR.

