*Hypothesis 2.1: Patients after ACLR will demonstrate increased CSE (lower AMTs and steeper SLOPEs) after one session of active tDCS and no changes in CSE after placebo tDCS.*

*Hypothesis 2.2: Patients after ACLR will demonstrate greater RTD/isometric strength after one session of active tDCS and no changes in RTD/isometric strength after placebo tDCS.*

**Aim 2:** Determine the relationship between two measures of CSE and two measures of quadriceps muscle performance in patients after ACLR.

*Hypothesis 1.1: Greater CSE will be associated with greater quadriceps isometric strength and greater RTD.*

*Hypothesis 1.2: The correlation between CSE and RTD will be greater than the correlation between CSE and isometric strength.*

*Current outcomes following ACLR are less than optimal with patients demonstrating chronic quadriceps dysfunction related to altered movement patterns and the development of post-traumatic knee OA. Emerging evidence suggests that quadriceps dysfunction after ACLR is related to alterations in CSE. Therefore, interventions targeting CSE have the*

*potential to mitigate chronic quadriceps dysfunction, improve movement patterns, and improve outcomes. The proposed study is a logical and essential first step in determining the effect of tDCS, an intervention known to induce changes in excitability, on CSE and quadriceps performance in patients after ACLR. Upon completion of this study, I will have obtained the pilot data needed to apply for a larger grant to investigate the effects of multiple sessions of tDCS on CSE and quadriceps muscle performance, generating the evidence needed to introduce this intervention into the clinical practice.*

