**Anticipated date of Submission:**

**b) Is this a collaboration with another institution (if yes, please move to section 3 c)?**

- Yes
- No

**c) Is each institution doing their own review or will one institution serve as the primary IRB through an Authorization Agreement?**

- Each institution will complete their own review.
- An Authorization Agreement will be signed.

**4. Study Population - Are the human subjects involved in the proposed activity included in the following categories? (check all that apply, at least one box must be checked)**

*Yes. Human subjects are included in this study.*

 Minors	 Pregnant women, human fetuses, neonates
 Prisoners	 AIDS/HIV-positive subjects
 Terminally ill subjects	 Subjects with intellectual disabilities
 Economically and/or educationally disadvantaged persons	 Minorities
 None of the above	 Other Click here to enter text.

**5. Inclusion and Exclusion Criteria - Describe the criteria that define who will be included or excluded in your study sample. If you are conducting data analysis only describe what is included in the data set you propose to use.**

*ACLR Group: Individuals between the ages of 13 and 55 years with a history of ACLR (4 months to 5 years) will be recruited.*

*Uninjured Group: Individuals between the ages of 13 and 55 years without a history of major knee injury or surgery will be recruited for the uninjured group. These participants will be matched to participants in the ACLR group by sex, age, and activity level.*

*Both groups must participate (or participated in prior to surgery) in sports involving jumping, pivoting, cutting on a regular basis to be included. Individuals < 18 years of age will only complete strength testing and questionnaires at one testing session. They will not participate in TMS testing or the intervention (tDCS with stationary bike riding).*

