**6. Number of Participants - Indicate the total number of anticipated participants to be recruited and enrolled.**

*Thirty subjects without a history of major knee injury/surgery and 30 subjects with a history of ACLR will be recruited for this study.*

**7. Recruitment Method - Describe who will be doing the recruitment of participants. Describe when, where, and how potential participants will be identified and recruited. Describe and attach materials that will be used to recruit participants (attach documents or recruitment script with the application).**

*The following recruitment methods will be used for this study.*

- a. *Two flyers have been created for recruitment (see attached, one flyer for uninjured participants and one for participants after ACLR). These flyers will be posted on bulletin boards at Arcadia University, posted on social media, emailed to students, and emailed to local physical therapists.*
- b. *Individuals with a history of ACL reconstruction will be recruited from local physical therapy clinics. Physical therapists will be notified of the study via email and/or phone and asked to have interested participants complete the "consent to contact form". Email/phone scripts are below. Good Sheppard/PENN Partners (GSPP) has a physical therapy clinic on campus. GSPP requires that a specific consent to contact form. Therefore, two consent to contact forms will be attached to this protocol. The physical therapists will only be informing the patients or patients guardians (if under 18 years old) that they may be eligible for a study being conducted at Arcadia University and having the patients/guardians complete the consent to contact form. Patients who complete the consent to contact form will be contacted by the PI who will determine eligibility and explain the study in more detail. Only the PI will be gaining consent with each subject.*

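### The stated limb-by-group ANOVA has no active/sham term and no pre/post term, so no analysis in the protocol answers Aim 1

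*Protocol*

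**What the plan says.** Section 1 of the protocol states Aim 1 as: "Determine the effects of a single session of tDCS on two measures of CSE and two measures of quadriceps performance in patients after ACLR". Two hypotheses follow it, numbered 2.1 and 2.2. For excitability, the first expects "increased CSE (lower AMTs and steeper SLOPEs) after one session of active tDCS and no changes in CSE after placebo tDCS". The second reads: "Patients after ACLR will demonstrate greater RTD/isometric strength after one session of active tDCS and no changes in RTD/isometric strength after placebo tDCS". The closing paragraph of section 1 gives the purpose: "The proposed study is a logical and essential first step in determining the effect of tDCS", with the results to serve as pilot data for a larger grant on repeated sessions.

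The procedures in section 8 match that question. There are two sessions at least 48 hours apart, testing takes place before and after stimulation, and the tDCS subsection describes an active and a sham form.

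The Data Analysis paragraph at the end of section 8 lists three things:

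- independent t-tests on demographics between the two groups;
- for the outcomes, "A 2 (limb) x 2 (group) ANOVA will be used to evaluate differences in strength, TMS, and fNIRS measures";
- regressions relating CNS measures to quadriceps strength, and TMS to fNIRS measures.

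Section 5 sets out the groups. One is people with a history of ACLR; the other is people "without a history of major knee injury or surgery will be recruited for the uninjured group". Section 6 gives their sizes: "Thirty subjects without a history of major knee injury/surgery and 30 subjects with a history of ACLR will be recruited for this study".

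**The concern.** Aim 1 concerns stimulation condition (active or sham) and time (before or after). The only outcome comparison in the protocol has limb and group as its factors, and group means ACLR or uninjured. Strength and the TMS measures are Aim 1 outcomes, yet they are assigned to a model that answers a different question: how ACLR and uninjured people differ, limb by limb.

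The tDCS estimate is what the pilot is meant to hand to the next grant. If the written plan were followed, that estimate would not be produced. If the analyst departed from it, the form of the main contrast (change score or adjusted post value, which limb, which participants) would be open to choice after the data were seen.

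**Working it through.** There is no stated figure to reproduce. The protocol gives 30 + 30 participants without alpha, power, effect size or SD. The check is whether the stated model can express the Aim 1 quantity.

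**Inputs.** Target: section 1, Aim 1 and Hypotheses 2.1 and 2.2. Factors collected: section 8, opening paragraph and tDCS subsection. Groups and numbers: sections 5 and 6. Model: section 8, Data Analysis.

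**Step 1, the target.** In ACLR participants,

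Δ = (active post − active pre) − (sham post − sham pre),

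with weights +1, −1, −1, +1 on the four condition-by-time cells.

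**Step 2, the stated model.** E(Y) = β0 + β1·limb + β2·group + β3·limb×group. Within one limb of one group nothing in the model varies with condition or time, so all four cells share one fitted mean m. Hence

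fitted Δ = (m − m) − (m − m) = 0,

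whatever the coefficients and whatever the sample size. Participant effects do not help: they are constant over time, and the post and pre weights within a participant and session sum to zero (+1 − 1 = 0). The same holds if each person receives only one condition.

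**Step 3, numerical confirmation.**

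- Cell level: group × limb × condition × time gives 2×2×2×2 = 16 cells. The stated model has rank 4. The Δ contrast for the ACLR surgical limb has length √(1+1+1+1) = 2.0, and its projection on the model has length 0.0.
- Cell level with condition, time and condition × time added: rank 7. The contrast averaged over the four group-by-limb combinations projects fully (1.0 of 1.0).
- Participant level, assuming everyone is stimulated: 60×2 limbs×2 sessions×2 times = 480 rows if each person has both conditions, or 60×2×2 = 240 if only one. The share of Δ captured was numerically 0 in all 16 settings (2 layouts × 4 sample sizes, 30+30, 25+25, 20+20 and 10+10 × with or without participant effects), and also with unequal arms of 12 and 18. After adding time, condition, condition × time and their ACLR-limb terms, the share was 1.00 throughout.

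**Step 4, in effect units.** Noise-free data:

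| True tDCS effect (SD) | Δ from stated model | Δ computed directly |
|---|---|---|
| 0 | 0.00 | 0.00 |
| 0.5 | 0.00 | 0.50 |
| 1.0 | 0.00 | 1.00 |

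A simulation (30 + 30, 2,000 runs per effect) used assumed values: between-person SD 0.9, within-person SD 0.45, surgical-limb deficit 0.8. At baseline the limb × group interaction averaged −0.796, −0.791 and −0.807 for true effects of 0, 0.5 and 1.0. It shows the limb deficit and nothing about tDCS. The direct contrast averaged 0.004, 0.503 and 1.002.

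**Step 5, pooling post-stimulation data.** Suppose each person receives both conditions, all four occasions are pooled, and an effect d occurs only in the ACLR surgical limb after active stimulation. That limb's mean then moves by (0+0+0+d)/4 = d/4, which is 0.125 for d = 0.5 and 0.25 for d = 1.0. The shift enters the limb × group term, so the ANOVA would be affected by tDCS without being able to identify it.

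**Step 6, other readings.**

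- Group as active versus sham: there is still no time term, and this conflicts with section 5 and with section 11, which uses the word for ACLR and uninjured.
- ANOVA on change scores: this absorbs time, but the text mentions no change scores, and ACLR versus uninjured still leaves out active versus sham.
- Regressions: these describe associations, which is Aim 2.

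Reaching Aim 1 takes both a redefined group and an unstated change score.

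**The case against.** The strongest reply is that this is an omission. The paragraph never calls the ANOVA the Aim 1 analysis, it includes fNIRS (which is in neither aim), and it reads well as a descriptive comparison of ACLR with uninjured participants. The form asks for a lay summary, and a statistical analysis plan not seen here might supply the missing contrast. The limb-by-group model is indeed legitimate for that descriptive purpose. But the protocol does name its outcome analyses, and none serves its first aim. An analysis plan that kept to the paragraph would inherit the mismatch; one that added the contrast would go beyond what the protocol states.

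Four narrower objections have substance:

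- The zero holds by construction. It shows that the stated model cannot express the effect; it does not measure a bias. The varied settings add reassurance but no further argument.
- The hypotheses are written as two within-condition statements, a change after active and none after placebo. The difference in change is the sound inference about tDCS, but it does not by itself test the no-change half.
- TMS covers both hemispheres and two tasks, possibly several muscle groups, and strength is tested in both legs. The contrast is a single quantity only once these are named.
- The protocol does not say outright who receives active or sham, or in which session, and the strength-testing text does not describe how RTD is derived.

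These points shape the remedy and leave the mismatch in place.

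**Conclusion.** The concern holds: the analysis is wrong as written for Aim 1. The protocol poses a condition-by-time question and plans both factors, then assigns the outcomes to a model containing neither. The share of the Aim 1 contrast that the stated model can recover is 0, against 1.00 once condition, time and their interaction are included.

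This rests on one reading, that group means ACLR versus uninjured, which sections 5 and 11 and the demographic t-tests support. It does not depend on sample size, on the simulation's assumed SDs, or on whether each person receives both conditions. What an unseen analysis plan might add cannot be judged here. The certainty therefore attaches to the protocol text, which must be corrected before analysis.

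**What to change.** In section 8, Data Analysis:

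1. Add an Aim 1 analysis in ACLR participants aged 18 or over who receive stimulation; section 5 keeps younger participants out of TMS and tDCS.
2. For AMT, SLOPE, isometric strength and RTD, estimate the active-minus-sham difference in pre-to-post change with its 95% CI. Choose one model in advance: a condition × time term, or the post value adjusted for that session's pre value. Include a participant effect where a person contributes repeated records.
3. Name the limb, hemisphere, task and muscle for each outcome. The surgical limb and the stimulated hemisphere are the natural choices given the tDCS subsection. Say how RTD is derived.
4. State whether each participant receives both conditions and how the condition is allocated. If both, add period and sequence to the model.
5. Judge Hypotheses 2.1 and 2.2 by the difference in change. Also report the change within each condition with its CI; a non-significant change after sham would not in itself show that there was none.
6. Keep the limb-by-group ANOVA for the ACLR-versus-uninjured comparison, limited to the session 1 pre-test, before any stimulation.

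The cost is a few sentences and a few lines of code. Pre and post testing and both forms of stimulation are already planned, so no visit is added. The allocation statement in item 4 needs a decision from the investigator as well as wording.

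### Data Analysis does not name RTD, compare the two correlations of Hypothesis 1.2, or include pre/post or active/sham, so Hypotheses 1.2, 2.1, 2.2 and the RTD half of 1.1 are not tested as written

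*Protocol*

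**What the plan says.** Section 1 (Background and Objectives) commits the study to two outcomes: "We will incorporate two measures of quadriceps performance, isometric strength and rate of torque development (RTD". It defines excitability (CSE) by active motor threshold (AMT) and recruitment-curve slope (SLOPE). The hypotheses that use RTD are:

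- Hypothesis 1.1 predicts an association with both outcomes: "Greater CSE will be associated with greater quadriceps isometric strength and greater RTD".
- Hypothesis 1.2 ranks the two associations: "The correlation between CSE and RTD will be greater than the correlation between CSE and isometric strength".
- Hypothesis 2.2 concerns the effect of stimulation: "Patients after ACLR will demonstrate greater RTD/isometric strength after one session of active tDCS and no changes in RTD/isometric strength after placebo tDCS".

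Hypothesis 2.1 makes the matching claim for CSE, with an increase meaning "lower AMTs and steeper SLOPEs". In the protocol, Hypotheses 2.1 and 2.2 stand under Aim 1, and 1.1 and 1.2 under Aim 2.

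In section 8, Strength testing describes three recorded maximal isometric contractions and the recording of the force or torque produced. It does not mention RTD. Data Analysis has three parts: t-tests on demographics between the two groups; an ANOVA with two limbs and two groups for strength, TMS and fNIRS measures; and regressions. On quadriceps function the regression sentence reads "Regression analyses will be used to determine the relationship between the CNS measures and quadriceps strength"; a second regression relates TMS to fNIRS.

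**The concern.** RTD is one of only two quadriceps outcomes, and three of the four hypotheses rest on it, yet it drops out of the text after the hypotheses. Hypothesis 1.2 is a claim about the difference between two correlations, and no such comparison is stated. The tDCS hypotheses concern change from before to after stimulation under active and placebo conditions, but the only model stated for group differences has neither of those factors.

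Followed literally, the plan would deliver a comparison of limbs and groups and a set of strength regressions. It would leave the main stimulation question and the RTD questions without a specified analysis. The choice of analysis would then be made later, possibly with data in hand.

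**Working it through.** There is no stated figure to reproduce, so the check sets each hypothesis beside the analysis that is stated for it.

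| Hypothesis | What it needs | What Data Analysis states | Covered |
|---|---|---|---|
| 1.1 | AMT and SLOPE, each with strength and RTD: 2 × 2 = 4 associations | Regressions of CNS measures and quadriceps strength | 2 of 4 |
| 1.2 | For each CSE measure, correlation with RTD minus correlation with strength: 2 comparisons | Nothing | 0 of 2 |
| 2.1 | Pre/post change, active against sham, for AMT and SLOPE: 2 outcomes | Limb-by-group ANOVA | 0 of 2 |
| 2.2 | The same for strength and RTD: 2 outcomes | Limb-by-group ANOVA | 0 of 2 |

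**Regressions.** Section 1 lists strength and RTD as separate measures, and Hypothesis 1.2 contrasts them. The natural reading of quadriceps strength in the regression sentence is therefore the strength measure alone. AMT and SLOPE are not named in Data Analysis either, but both come from TMS and fall under CNS measures, so they are counted as covered.

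**Hypothesis 1.2.** The quantity of interest is d = r(CSE, RTD) − r(CSE, strength). Both correlations come from the same people and share the CSE measure, so

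Var(d) = Var(r1) + Var(r2) − 2 Cov(r1, r2),

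and the covariance depends on the correlation between RTD and strength. Two separate regressions supply r1 and r2 but not the covariance. Adding RTD to the regressions would thus complete Hypothesis 1.1 but still not test Hypothesis 1.2. One association reaching significance while the other does not is not evidence that they differ.

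**ANOVA.** A model with limb and group gives three effects: limb, group and their interaction. Section 5 defines the groups as ACLR and uninjured. Hypotheses 2.1 and 2.2 need an effect of time by stimulation condition, and section 8 provides pre and post testing and active and sham stimulation. None of the three effects contains either factor. This gap applies to every outcome, not only RTD.

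**Sensitivity to wording.** If strength in the regression sentence is read generously to include RTD, Hypothesis 1.1 moves from 2 of 4 to 4 of 4. Hypothesis 1.2 stays at 0 of 2, and Hypotheses 2.1 and 2.2 together stay at 0 of 4.

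**Who contributes.** Section 6 says "30 subjects with a history of ACLR will be recruited for this study". Participants under 18 have no TMS and no intervention, so at most 30 ACLR participants can inform these hypotheses, and fewer if minors enrol.

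**The case against.** The strongest reply is that this is an IRB form written as a lay summary, that a separate SAP may exist, and that naming RTD in a regression or choosing a test for dependent correlations is ordinary SAP content. Part of this stands: the technical form of the test, the RTD time window and the onset rule can all wait for an SAP. But the protocol has its own Data Analysis section, and the analyses it states do not answer the hypotheses it states. A model with the wrong factors is a mismatch, not just brevity.

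A second reply is that Data Analysis uses labels by type of test, so strength measures in the ANOVA sentence may be shorthand for everything from the strength session, RTD included. That reading is open, and a reader should not infer that RTD is excluded there. It is weaker for the regression sentence, which names quadriceps strength. It does not rescue the ANOVA, which lacks the needed factors whatever outcomes go into it. Running the ANOVA on change scores, which is not stated, would still leave out active versus sham.

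A reader might also infer that RTD will not be collected, or will be lost. The documents do not support this. The contractions are recorded for analysis, which may include the torque-time trace, and a lay description of the effort need not be the test script. What can be said is only that the protocol does not state how RTD is obtained.

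**Conclusion.** The point holds. As written, Data Analysis does not test Hypothesis 1.2 or the RTD half of Hypothesis 1.1, and its ANOVA cannot test Hypothesis 2.1 or 2.2 for any of the four outcomes. Only the two associations with isometric strength have a matching analysis. The silence of Strength testing on RTD is a lesser, conditional part of the point: an SAP can add an analysis later, but it cannot restore a signal that was not kept.

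The conclusion rests on two readings: that quadriceps strength in the regression sentence means the strength measure, and that group means ACLR versus uninjured. Relaxing the first changes only Hypothesis 1.1. Section 1 calls this a pilot study, which lowers the need for formal testing but not the need for analyses that address the stated questions.

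A reader might go further and conclude that the sample is too small to settle Hypothesis 1.2. The documents give no correlations, so any power or precision figure would rest wholly on assumed values and would not measure this defect. No such claim is made here.

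**What to change.** 1. **Data Analysis, regressions and stimulation effect.** Name RTD beside isometric strength in the regressions. Add an analysis that compares pre/post change between active and sham sessions for AMT, SLOPE, isometric strength and RTD. This takes the two collections to be one active and one sham session per participant, which the text implies; the section should say so.
2. **Data Analysis, Hypothesis 1.2.** In ACLR adults with TMS data, report the difference between the two dependent correlations with a 95% CI, once for AMT and once for SLOPE. Reverse the sign of AMT, since a lower threshold means greater excitability.
3. **Strength testing.** State that the torque-time trace of the maximal contractions is kept for RTD, and that the contraction instruction used for RTD is the same at every pre and post test. The wording is for the investigator to decide.

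The cost is a few sentences, slightly more analysis work and a stored trace, with no added visits or procedures. The main risk is that a change of instruction may shift peak torque, and with it the isometric-strength outcome and the 5% target used during TMS. Any change must therefore be applied uniformly, and anyone already tested under a different instruction should be identified. The documents do not say whether testing has begun or whether the dynamometer exports a usable trace; both should be checked first.
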